## **STUDY DESIGN**

**Subjects:** Pediatric patients aged 7-17 years presenting to the ED with acute painful conditions such as traumatic and non-traumatic abdominal, flank, back, musculoskeletal pain, vaso-occlusive painful crisis of sickle cell disease, and lacerations with a pain score of 5 or more on a standard 11- point (0 to 10) numeric rating scale and requiring sub-dissociative dose ketamine analgesia as determined by the treating

attending physician. Eligible patients will be identified by the primary evaluation of the treating physician, who believes that the patient will benefit from the non-invasive route of Breath Actuated Nebulized (BAN) Sub-Dissociative Dose Ketamine rather than other methods (Intravenous, oral etc.) The treating physician will inform the research team of the potential patient to begin the consenting and enrollment process.

Patients' screening and enrollment will be performed by study investigators and research assistants. All patients will be enrolled at various times of the day when study investigators will be available for patient enrollment and ED pharmacists will be available for medication preparation.

**Eligibility Criteria:** Patients with ages between 7 and 17 presenting to the ED with acute painful conditions such as traumatic and non-traumatic abdominal, flank, back, musculoskeletal pain, vaso-occlusive painful crisis of sickle cell disease, and lacerations with a score of 5 or more on a standard 11- point (0 to 10) numeric rating scale. Patients receiving oral acetaminophen and/or ibuprofen at triage prior to SDK administration will be eligible for the study.

**Exclusion criteria** will include altered mental status, GCS<15, allergy to ketamine, pregnant patients, weight greater than 100 kg, heart rate >180, airway abnormalities (congenital or acquired), absence of parent(s) at the time of consent, closed head injury, seizure disorder, use of opioid analgesics, schizophrenia or bipolar disorder.

**Design:** This is a prospective, randomized, double-blind trial comparing analgesic efficacy and safety of nebulized SDK administered at three different doses to pediatric patients presenting to the ED of Maimonides Medical Center with acute painful conditions. Upon meeting the eligibility criteria, patients will be randomized into one of three study arms based on the dosing of the SDK: 0.75 mg/kg, 1 mg/kg, and 1.5 mg/kg.

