**Data Collection Procedures:** Each patient will be approached by a study investigator for acquisition of written informed consent and Health Insurance Portability and Accountability Act authorization after being evaluated by the treating emergency physician and determined to meet study eligibility criteria. When English will not be the participant's primary language, a staff interpreter or licensed telephone interpreter would be used. Baseline pain score will be determined with an 11-point numeric rating scale (0 to 10), described to the patient as "no pain" being 0 and "the worst pain imaginable" being 10. A study investigator will record the patient's body weight and baseline vital signs. The on-duty ED pharmacist will prepare a breath-actuated nebulizer with doses of 0.75 mg/kg, 1 mg/kg, and 1.5 mg/kg according to the predetermined randomization list, which will be created in SPSS (version 24; IBM Corp, Armonk, NY) with block randomization of every 10 participants. The medication will be delivered to the treating nurse in a blinded fashion and will be administered via breath-initiated nebulization for duration of treatment of 10 minutes.

Study investigators will record pain scores, vital signs, and adverse effects at 15, 30, and 60 minutes. In addition, study investigators will record a residual amount of medication (ml) in the nebulizer after the treatment.

If patients reported a pain numeric rating scale score of 5 or greater and requested additional pain relief at 15 minutes mark post-ketamine administration, intravenous morphine at 0.1 mg/kg will be administered as a rescue analgesic.

All data will be recorded on data collection sheets, including patients' sex, demographics, medical history, and vital signs and entered into SPSS (version 24.0; IBM Corp) by the research manager. Development of the randomization list, confirmation of written consent acquisition for all participants, and statistical analyses will be conducted by the research manager and statistician, who would work independent of any data collection.

Patients will be closely monitored for any change in vital signs and for adverse effects during the entire study period (up to 2 h) by study investigators. Common adverse effects that are associated with sub-dissociative dose ketamine are feeling of unreality, dizziness, nausea, vomiting, and sedation.

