**Data Analysis:** Data analyses will include frequency distributions, paired t-test to assess a difference in pain scores within each group, and independent-sample t-test to assess differences in pain scores between the 3 groups at the various intervals.

Mixed-model linear regression will be used to compare changes in pain numeric rating scale across time points. This will compensate for participants lost to follow-up and allow all patients' data to be analyzed on an intention-to-treat principle.

For categorical outcomes (eg, complete resolution of pain), a  $X^2$  or Fisher's exact test will be used to compare outcomes at 30 minutes. Percentage differences and 95% confidence intervals between the treatment groups will be calculated for all time points with  $P < .05$  to denote statistical significance. Based on the validation of a verbally administered rating scale of acute pain in the ED and the comparison of verbal and visual pain scales, we will use a primary outcome consisting of a minimal clinically meaningful difference of 1.3 between three groups at the 30-minute pain assessment.

**Expected Outcomes:** The primary outcome will include a comparative reduction in pain scores on numeric rating pain scale (NRS) between recipients of nebulized SDK given at three different doses at 15 minutes after analgesic administration. The secondary outcomes will include a need for rescue analgesia at 15, 30 or 60 minutes and adverse events in each group.

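### Pain cause and age are known before randomization but have no role in the dose comparison, so some precision may be lost and no adjustment for chance imbalance is prespecified

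*Combined protocol and SAP*

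**What the plan says.** All of the relevant text is under STUDY DESIGN in the combined protocol and SAP.

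- **Population.** The Subjects paragraph admits "Pediatric patients aged 7-17 years presenting to the ED with acute painful conditions", covering "traumatic and non-traumatic abdominal, flank, back, musculoskeletal pain, vaso-occlusive painful crisis of sickle cell disease, and lacerations".
- **Randomization.** The Data Collection Procedures paragraph describes one predetermined list with "block randomization of every 10 participants". It names no stratification factor.
- **Data recorded.** "All data will be recorded on data collection sheets, including patients' sex, demographics, medical history, and vital signs". Age would ordinarily fall under demographics. Pain cause is not named, although the list is not exhaustive. Baseline NRS is measured.
- **Analysis.** The Data Analysis paragraph plans an "independent-sample t-test to assess differences in pain scores between the 3 groups at the various intervals". It adds: "Mixed-model linear regression will be used to compare changes in pain numeric rating scale across time points". No model terms are listed.

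Pain cause and age are not named as a stratum, covariate or subgroup anywhere in the document.

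**The concern.** A laceration and a sickle-cell crisis may respond differently to the same analgesic, and a 7-year-old may use a 0 to 10 scale differently from a 17-year-old. If so, part of the spread in the 15-minute reduction is predictable from facts known at entry. An unadjusted comparison leaves that part in the error term.

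The trial compares three active doses, so the differences of interest may be modest and precision matters. Credibility is also at stake. If one arm happens to receive more of a poorly responding condition, the plan has no adjustment ready, and one chosen after the imbalance is seen would be open to a charge of selection.

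**Working it through.** The documents state no sample size, power or SD, so there is no planned figure to reproduce. The calculation below is illustrative.

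**Inputs from the documents.** A difference of 1.3 NRS points (Data Analysis, where it is tied to the 30-minute assessment although the primary outcome is at 15 minutes), significance at 0.05, and three arms.

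**Assumed inputs.** Two-sided testing, equal allocation, 40 per arm (120 in all), SD 2.5, sickle-cell crisis in 20% of patients, and a 1.5-point smaller reduction in that group.

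**1. Variance explained by cause.** p(1 − p) × effect² / SD² = 0.2 × 0.8 × 1.5² / 2.5² = 0.36 / 6.25 = 0.058, or about 6%.

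**2. Power of one dose contrast.** The standard error is 2.5 × √(2/40) = 0.56. Unadjusted power from the noncentral t with 78 degrees of freedom is 63.2%. With the SD reduced to 2.5 × √(1 − 0.058), power is 65.8%.

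**3. Cost of the added terms.** Cause in three groups uses two degrees of freedom and age uses one. With 120 patients and three arms, the variance of a dose contrast rises by about 3/113 = 2.7%. The net variance factor is 0.942 × 1.027 = 0.967, which gives power of 64.6%. The net gain in this example is therefore between one and two points.

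**4. Sensitivity to prognostic strength.** Power before the degrees-of-freedom cost, at 40 per arm:

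| Variance explained by cause and age | Variance factor 1/(1 − R²) | Power |
|---|---|---|
| 0% | 1.00 | 63.2% |
| 5% | 1.05 | 65.4% |
| 10% | 1.11 | 67.8% |
| 20% | 1.25 | 72.8% |

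The last two rows need more prognostic strength than the sickle-cell example supplies.

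**5. Chance imbalance.** The 95% range for the difference in sickle-cell share between two arms is ±1.96 × √(2 × 0.2 × 0.8 / 40) = ±17.5 percentage points. The exact binomial probability that two given arms differ by 15 points or more is 12%. By simulation, the probability that at least one of the three pairs does so is about 27%. A 17.5-point imbalance moves the unadjusted contrast by 0.175 × 1.5 = 0.26 points. That is 20% of 1.3, but only 0.26 / 0.56 = 0.47 of one standard error. The standard deviation of the shift is 0.13 points.

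**6. Validity of the unadjusted test.** A simulation with an omitted prognostic factor (50 per arm, 30% prevalence, 2-point effect, 40,000 runs) gave a type I error of 5.0%.

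**The case against.** The strongest reply is that nothing is broken. Randomization makes the unadjusted contrast unbiased, and variation due to chance imbalance is already in its standard error. A reader might infer from the 0.26-point shift that the t-tests carry an uncorrected error, or that imbalance is a second cost on top of lost precision. Neither is supported: the type I error stays at 5%, the shift is a 95%-limit figure of about half a standard error, and it is the same cost seen from another side. That part of the objection stands in full.

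A reader might also expect a gain of five to ten power points. The documents do not support that either. They say nothing about how well cause or age predicts the 15-minute reduction, and no age effect has been quantified here. Nor does the plan rule covariates out; it lists no terms for the mixed model.

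It is also fair to say that the Data Analysis paragraph has more basic gaps: the primary time point is 15 minutes in one place and 30 in another, and no sample size is given. Covariates are a refinement beside these.

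What survives is that a better method is available at almost no cost. The factors are fixed before randomization, the model family is already planned, and silence on its terms leaves the choice open until outcomes are known.

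**Conclusion.** The point holds as one of efficiency and prespecification, not of validity. The planned t-tests are sound but ignore pain cause and age in a mixed population. Some precision may be lost, and no adjustment for an imbalance is fixed in advance.

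The likely size is small. In the worked example power moves from about 63% to 66%, less about one point for three degrees of freedom. Gains are larger only if cause and age together predict more strongly than that example assumes; if they predict nothing, adjustment costs about one point of power. Every input except the 1.3-point difference and the 0.05 level is an assumption. The change is worth making because it is cheap, but the trial does not depend on it.

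**What to change.** Keep the randomization unstratified; many causes would leave sparse strata. In Data Analysis:

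- Name one primary between-dose model of the 15-minute pain-score reduction, namely the mixed model already planned.
- Prespecify its covariates in one sentence: baseline NRS, age in years, and pain cause in three fixed groups (sickle-cell crisis; trauma including laceration; other non-traumatic pain).
- State that the adjusted estimate is primary and that the unadjusted comparison is supportive.

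Add pain cause to the data collection sheet as its own field, completed before randomization.

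The cost is a short addition to the analysis text, one data field, and three degrees of freedom for cause and age plus one for baseline NRS. If these factors turn out not to be prognostic, precision falls slightly.

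### Low-priority improvement, not an error: need for rescue at 15 minutes is compared without adjustment, although baseline pain score is recorded and is a likely predictor of it

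*Combined protocol and SAP*

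**What the plan says.** All of this is under STUDY DESIGN in the combined protocol and SAP.

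- **Outcome (Expected Outcomes).** "The secondary outcomes will include a need for rescue analgesia at 15, 30 or 60 minutes and adverse events in each group".
- **Rescue rule (Data Collection Procedures).** "If patients reported a pain numeric rating scale score of 5 or greater and requested additional pain relief at 15 minutes mark" after ketamine, intravenous morphine is given. Rescue therefore needs both a score threshold and a request.
- **Entry (Eligibility Criteria).** The listed conditions end with "lacerations with a score of 5 or more on a standard 11- point (0 to 10) numeric rating scale", so baseline scores run from 5 to 10.
- **Baseline measurement (Data Collection Procedures).** "Baseline pain score will be determined with an 11-point numeric rating scale (0 to 10"), taken before dosing.
- **Categorical outcomes (Data Analysis).** A chi-square or Fisher's "exact test will be used to compare outcomes at 30 minutes". The estimation sentence is wider: "Percentage differences and 95% confidence intervals between the treatment groups will be calculated for all time points". Neither names a covariate. Rescue is not mentioned by name here, but it is a categorical outcome.
- **Regression (Data Analysis).** "Mixed-model linear regression will be used to compare changes in pain numeric rating scale across time points". This is the only model, and it is for pain scores, not for rescue.
- **Randomization (Data Collection Procedures).** A list "with block randomization of every 10 participants", with no stratification by baseline score described.

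**The concern.** The score part of the rescue rule is a threshold on a second reading of the baseline scale. A child who enters at 10 has further to fall to get below 5 than one who enters at 5, so some dependence of rescue on baseline is likely. The plan collects the baseline score but describes no use of it for this outcome, either in the analysis or in the allocation.

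Two things are at stake, both modest. The crude difference may be less precise than it could be. And a chance difference between arms in mean baseline score would carry into the rescue difference. If the first adjusted analysis is devised after the data are seen, the choice of adjustment is also open to question.

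**Working it through.** **1. Inputs.** The plan states no figure on this point, so there is none to reproduce. From the documents: three dose arms, entry score 5-10, rescue threshold 5 plus a request, significance level 0.05 (two-sided assumed), and 1.3 points as the minimal clinically meaningful difference (stated for 30 minutes; borrowed here as the 15-minute difference between 1.5 and 0.75 mg/kg). Not in the documents, hence assumed: equal arms of 20, 40 or 60; residual SD 2; 60%, 80% or 100% of eligible children requesting; three baseline distributions on 5-10 (uniform, low-weighted, high-weighted); and the slope *b*, in points of 15-minute score per point of baseline, set at 0, 0.3, 0.5 or 1.

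**2. Does rescue depend on baseline?** Take mean baseline 7.5 and mean fall 3. The underlying 15-minute mean for entry score B is 4.5 + *b*(B - 7.5). A rounded score of 5 or more means an underlying value of at least 4.5, so P(score ≥ 5) = Φ(*b*(B - 7.5)/2).

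| Slope | Entry at 5 | Entry at 10 |
|---|---|---|
| 0 | Φ(0) = 50% | 50% |
| 0.3 | Φ(-0.375) = 35% | 65% |
| 0.5 | Φ(-0.625) = 27% | 73% |
| 1 | Φ(-1.25) = 11% | 89% |

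The shared cut-off of 5 does not create dependence; at slope 0 there is none. Tracking does.

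**3. Chance imbalance.** For a uniform baseline, SD = √(35/12) = 1.71. The difference in means of two arms of n has standard error 1.71 × √(2/n): 0.54, 0.38 and 0.31 at 20, 40 and 60. Over the three distributions, two given arms differ by 0.5 point or more in about 29-38%, 13-20% and 6-12% of trials. The effect on the crude rescue difference is roughly the average gradient times 0.5. At slope 1 with all requesting, (89 - 11)/5 × 0.5 = 7.8 percentage points; with 60% requesting, 7.8 × 0.6 = 4.7. Simulated shifts per 0.5 point are about 0 (slope 0), 1.4-3.0 (0.3), 2.6-4.8 (0.5) and 4.7-8.6 (1). After adjustment they are -0.3 to +0.4.

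**4. Precision and power.** Simulation used 10,000 replicates per setting, with mean falls of 2.5, 2.93 and 3.8 in the three arms (3.8 - 2.5 = 1.3). The adjusted analysis was a Firth logistic regression on dose and linear baseline, giving a standardised risk difference with a delta-method interval. The crude interval was Wald and the crude test Pearson chi-square.

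| Slope | CI width, adjusted/crude | Power change in points, 40-60 per arm |
|---|---|---|
| 0 | 1.00-1.05 | -1.9 to -0.1 |
| 0.3 | 0.98-1.04 | -1.5 to +0.8 |
| 0.5 | 0.95-1.03 | -0.8 to +3.3 |
| 1 | about 0.83-0.97 | +1.1 to +13.9 |

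At slope 1 the power change depends on requests: +9.1 to +13.9 if all request, +1.1 to +8.3 if 80% do, +1.3 to +3.2 if 60% do. With SD 1.5 or 2.5 at 40 per arm, the extremes are -2.7 (slope 0, SD 1.5, 60% requesting) and +21.0 (slope 1, SD 1.5, all requesting); at slope 0.5 the top is +5.6.

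**5. Type I error.** With no dose effect, pairwise rejection was 0.039-0.061 crude and 0.044-0.055 adjusted. Among only those trials imbalanced by 0.5 point or more, crude rejection was 0.044-0.078 at slope 0.3 and 0.063-0.196 at slope 1; adjusted rejection over all slopes was 0.038-0.065.

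**6. The comparator at 20 per arm.** The plan names chi-square for 30 minutes only, so at 15 minutes the planned quantity is the percentage difference and its interval. Against chi-square, adjustment changed power by -1.9 to +9.6 points at 20 per arm. Against a crude Wald interval (uniform baseline) the change was -10.5 to +0.3, because that interval is liberal at this size (null rejection 6-8%). The sign depends on the comparator. At 40-60 per arm the choice matters little.

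**7. Cross-check by another route.** Assume rescue of 40% v 20%, baseline SD about 1.55, and an odds ratio per baseline point of 1.0, 1.3, 1.6, 2.0 or 2.5. The crude variance is (0.4 × 0.6 + 0.2 × 0.8)/n = 0.40/n. The ratio of adjusted to crude variance is 1.00, 0.97, 0.91, 0.83 and 0.75; square roots give width ratios of 1.00, 0.98, 0.95, 0.91 and 0.87. At 50 per arm, power moves from 59% to 59%, 60%, 63%, 67% and 72%. The pattern is the same.

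**8. Few events.** With 3 to 23 rescues in total, the Firth analysis rejected a true null at 0.007-0.049, with coverage 0.951-0.993: valid, but conservative.

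**The case against.** The best case against acting is that nothing here is wrong. The crude difference is unbiased under randomization, its overall error rate is near nominal, and the same remark fits almost any trial with a binary secondary outcome and a recorded baseline. The size of any benefit is not shown for this trial, since every input that drives it is assumed. At slopes up to 0.5 with 60-80% requesting, the power change is only -1.8 to +3.0 points. Gains measured against a chi-square test that the plan does not name for 15 minutes flatter the adjusted analysis at 20 per arm. And a penalised model with standardised differences is a good deal of method for one time point of one secondary outcome, in a plan that names only SPSS 24.

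Most of this stands, and it sets the priority: low. It does not remove the point, because the change needs no new data and its downside is small and bounded.

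A reader might go further and infer three things that the documents do not support:

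- **That equal thresholds for entry and rescue make rescue depend on baseline.** They do not; step 2 gives 50% v 50% at slope 0.
- **That the planned comparison is biased or invalid.** Randomization protects it. The inflated rejection in step 5 is conditional on an imbalance that has already occurred.
- **That the trial forgoes a material amount of power.** No sample size, variability, slope or request rate is given, so the trial cannot be placed in the region where the gain is large.

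**Conclusion.** The point holds as a cheap, low-priority improvement. The plan analyses 15-minute rescue only by unadjusted methods while recording a likely predictor. If tracking is strong, adjustment can narrow the interval by up to about 17%; if there is none, it gains nothing and may widen it by up to about 5%. At SD 2 and 40-60 per arm, the power change lies between about -2 and +14 points, and gains above about 5 appear only with strong tracking and a high request rate. At 20 per arm no reliable gain should be claimed. The steadier benefit is that a chance baseline imbalance no longer shifts the rescue difference appreciably.

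All sizes rest on assumed sample size, variability, baseline distribution, slope and request rate. What rests on the documents alone is that baseline score is recorded, that the methods described for categorical outcomes are unadjusted, and that the one model is for pain scores.

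**What to change.** Leave the rescue rule as it is. Add to Data Analysis: need for rescue at 15 minutes will be compared between doses by Firth logistic regression with dose (three levels) and baseline NRS as a linear term, reported as standardised (marginal) risk differences with 95% confidence intervals; crude percentages and differences will be shown alongside. Use the Firth fit throughout, with no event-count trigger, so that no choice of method is left until the data are in. The standardised risk difference keeps the effect measure in line with the percentage differences already planned; an adjusted odds ratio alone would not.

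Cost: one or two sentences and a little more analysis work, possibly a short script for the standardised differences. No new data, patients or staff. If baseline score is uninformative or few children request rescue, expect a loss of about 1-2 power points (2.7 in the worst setting tried), and conservative intervals when events are very few.

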## **HYPOTHESIS**

In our study we hypothesize that sub-dissociative-dose ketamine administered as a single agent via breath actuated nebulizer at the dose of 1.5 mg/kg will provide better analgesia at 15 min post-administration with similar rates of side effects in comparison to 0.75 mg/kg and 1 mg/kg for pediatric ED patients presenting to the ED with acute painful conditions. The primary outcome of this trial is the comparative reduction in participant’s pain scores at 15 minutes post medication administration.

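### The primary pain outcome is set at 15 minutes in the Hypothesis and Expected Outcomes but at 30 minutes in Data Analysis, and nothing ranks the two times

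*Combined protocol and SAP*

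**What the plan says.** Three statements name a primary outcome, and they do not agree on when it is measured.

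- **Hypothesis:** "The primary outcome of this trial is the comparative reduction in participant’s pain scores at 15 minutes post medication administration". The hypothesis itself uses the same time: the 1.5 mg/kg dose "will provide better analgesia at 15 min post-administration with similar rates of side effects in comparison to 0.75 mg/kg and 1 mg/kg".
- **Study Design, Expected Outcomes:** the primary outcome is a comparative reduction in numeric rating scale scores "between recipients of nebulized SDK given at three different doses at 15 minutes after analgesic administration".
- **Study Design, Data Analysis:** "we will use a primary outcome consisting of a minimal clinically meaningful difference of 1.3 between three groups at the 30-minute pain assessment".

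Data Analysis also places the test for categorical outcomes, such as complete resolution of pain, at 30 minutes: "exact test will be used to compare outcomes at 30 minutes". The secondary outcomes listed are need for rescue analgesia and adverse events. Pain at 30 minutes is not among them.

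Data Collection Procedures sets the measurement times: "Study investigators will record pain scores, vital signs, and adverse effects at 15, 30, and 60 minutes". The same section provides intravenous morphine for patients who score 5 or more and "requested additional pain relief at 15 minutes mark post-ketamine administration".

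**The concern.** Two times carry the label of primary outcome, and only one of them can decide whether the trial has met its aim. Someone working from the Hypothesis would take 15 minutes. Someone working from Data Analysis alone, where an analyst would look, would take 30 minutes.

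The times also measure different things. The 15-minute score helps to decide who may receive rescue, so for those patients it comes before the morphine. The 30-minute score can include the morphine. If rescue were used more in the lower-dose arms, a dose difference present at 15 minutes could be narrowed or hidden at 30 minutes, so the two times could lead to different conclusions.

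The 1.3-point difference is the only yardstick the plan gives for a meaningful result. As written, it applies to 30 minutes, which leaves the 15-minute hypothesis without one.

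**Working it through.** **Step 1. Compare the statements.**

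| Place | Status given | Time | Measure |
|---|---|---|---|
| Hypothesis, hypothesis sentence | hypothesis | 15 min | better analgesia, 1.5 mg/kg vs 0.75 and 1 mg/kg |
| Hypothesis, outcome sentence | primary | 15 min | comparative reduction in pain score |
| Expected Outcomes | primary | 15 min | comparative reduction in pain score |
| Data Analysis, 1.3-point sentence | primary | 30 min | difference of 1.3 between three groups |
| Data Analysis, categorical outcomes | none stated | 30 min | e.g. complete resolution of pain |

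Two of the three primary-outcome statements, and the hypothesis, say 15 minutes. The third says 30.

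**Step 2. Look for a rule that settles it.** The t-tests are planned at the various intervals and the mixed model runs across time points; neither names a primary time. The secondary outcomes do not include 30-minute pain. All of this is current text, and no redaction explains the difference.

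**Step 3. Ask whether 1.3 belongs to 30 minutes in particular.** Its stated basis is validation of a verbal rating scale and comparison of pain scales, and nothing in the text limits it to that time. The sentence cites references 28 and 29, but the reference list as supplied ends at 13, so the basis cannot be checked.

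**Step 4. Worst-case error rate.** The plan gives no sample size, standard deviation or power, so there is no figure of its own to reproduce. The assumptions are:

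- no true dose difference and equal arms;
- a two-sided test at 0.05 for each comparison (the plan states P < .05 in its percentage-difference sentence, and I assume it also applies to the pain comparison);
- a 15/30-minute correlation r, which is not in the documents;
- success claimed if either time is significant.

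For one dose pair, P(either) = 0.05 + 0.05 − P(both). P(both) comes from the bivariate normal distribution with correlation r and critical values ±1.96.

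| r | P(both) | P(either) | Increase over 5% |
|---|---|---|---|
| 0 | 0.25% | 9.75% | 4.75 points |
| 0.5 | 0.93% | 9.07% | 4.07 points |
| 0.7 | 1.65% | 8.35% | 3.35 points |
| 0.85 | 2.54% | 7.46% | 2.46 points |
| 0.9 | 2.96% | 7.04% | 2.04 points |

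Simulation with 2,000,000 replicates per value of r extends this to several unadjusted dose pairs:

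| Dose pairs | One time | Either time, r = 0.85 to 0.5 |
|---|---|---|
| Two in the hypothesis (1.5 vs 0.75, 1.5 vs 1 mg/kg) | about 9.1% | about 13.4% to 16.1% |
| All three | about 12.2% | about 17.7% to 21.3% |

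The 9.1% and 12.2% starting values come from testing several dose pairs, which is a separate issue. Only the rise above them belongs to this point. Using t-tests with 20, 40 or 60 per arm changes each rate by no more than 0.25 points.

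**Step 5. Rescue effect.** The documents give no basis for sizing it, so I put no number on it.

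**The case against.** The best reply is that this is a drafting slip with an obvious resolution. The Hypothesis section is definite, Expected Outcomes repeats it, and the outlier is a single sentence whose main purpose is to introduce the 1.3-point difference. Pain will be compared at every interval whichever time is primary, so no analysis is lost. The error rates require the choice to stay open until data are seen, which no passage says, and they rest on an assumed correlation. They also treat separate t-tests as the decision rule, although a mixed model is planned too. The categorical test at 30 minutes contradicts nothing, because that outcome is never called primary.

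Much of this is fair. A slip is plausible, the error rates are a worst case rather than a forecast, and the categorical test is only context. It is also true that both comparisons can be run; the conflict is over which one carries the primary claim.

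That claim is what a primary outcome exists to fix, however. The 30-minute sentence is in the analysis text and holds the only meaningful difference. The documents cannot show that it is a slip. Even if it is, the text stays contradictory until corrected.

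Two further remarks stand. Co-primary times with an alpha rule would also remove the contradiction, if that is what the sponsor intends. And changing the time leaves two descriptions of the measure: a comparative reduction, and a difference of 1.3 between three groups.

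**Conclusion.** The concern holds, and the plan must be corrected. The primary pain outcome is placed at two different times and nothing in the plan chooses between them. This rests on the text alone and needs no assumption. Because rescue can fall between the two times, the choice can change the trial's conclusion; by how much cannot be estimated from the documents.

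The error-rate figure is secondary. For one dose pair it is an increase of about 2.5 to 4 percentage points over 5%, for assumed correlations of 0.85 to 0.5. It applies only if the time is chosen after seeing data, with each time tested at 0.05. It is not the trial's expected error rate.

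**What to change.** Before any unblinded analysis, the sponsor should confirm one primary time and use it throughout. Consistent with the hypothesis and two of the three primary-outcome statements:

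1. In Data Analysis, in the sentence on the 1.3-point difference, replace the 30-minute assessment with the 15-minute assessment, so that 1.3 applies to the comparison the hypothesis makes.
2. Add one sentence stating that the 30- and 60-minute pain scores are non-primary.

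The cost is one phrase and one sentence. Pain is already recorded at 15, 30 and 60 minutes, so visits, data collected and patient management stay as they are.

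This settles the time point only. The primary dose contrast, the test that decides it, the handling of several dose pairs and the exact form of the measure still need to be stated.
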